**Table 2 – Time point response: patients with non-target disease only.**

Non-target lesions	New lesions	Overall response
CR	No	CR
Non-CR/non-PD	No	Non-CR/non-PD a
Not all evaluated	No	NE
Unequivocal PD	Yes or No	PD
Any	Yes	PD

CR = complete response, PD = progressive disease, and NE = inevaluable.  
a a 'Non-CR/non-PD' is preferred over 'stable disease' for non-target disease since SD is increasingly used as endpoint for assessment of efficacy in some trials so to assign this category when no lesions can be measured is not advised.

**Table 3 – Best overall response when confirmation of CR and PR required.**

Overall response First time point	Overall response Subsequent time point	BEST overall response
CR	CR	CR
CR	PR	SD, PD or PR a
CR	SD	SD provided minimum criteria for SD duration met, otherwise, PD
CR	PD	SD provided minimum criteria for SD duration met, otherwise, PD
CR	NE	SD provided minimum criteria for SD duration met, otherwise NE
PR	CR	PR
PR	PR	PR
PR	SD	SD
PR	PD	SD provided minimum criteria for SD duration met, otherwise, PD
PR	NE	SD provided minimum criteria for SD duration met, otherwise NE
NE	NE	NE

CR = complete response, PR = partial response, SD = stable disease, PD = progressive disease, and NE = inevaluable.  
 a If a CR is truly met at first time point, then any disease seen at a subsequent time point, even disease meeting PR criteria relative to baseline, makes the disease PD at that point (since disease must have reappeared after CR). Best response would depend on whether minimum duration for SD was met. However, sometimes 'CR' may be claimed when subsequent scans suggest small lesions were likely still present and in fact the patient had PR, not CR at the first time point. Under these circumstances, the original CR should be changed to PR and the best response is PR.

Reproduced from: Eisenhauer EA, Therasse P, Bogaerts J et al. New response evaluation criteria in solid tumors: revised RECIST guideline (version 1.1). Eur J Cancer. 2009;45:228-247.

## 13 ATTACHMENT 1: SUBSTANTIAL AMENDMENT 5

### I. The purpose of this amendment is:

Substantial Changes
1. Remove the Disease Assessment and Survival Assessment after the Safety Follow-up Visit
DESCRIPTION OF CHANGE:
“Disease Assessment” and “Survival” are removed from the study design and Flow Chart (Figure 1). These assessments will no longer be conducted after the Safety Follow-up visit.
RATIONALE:
Disease Assessment and Survival data will no longer be collected and analyzed.
2. Update the Schedule of Assessments (Table 1) and AGS-16C3F Pharmacokinetic Sampling Time Points (Table 2)
DESCRIPTION OF CHANGE:
The Schedule of Assessments is updated as follows: 
 
• Pharmacokinetics (AGS16C3F) is removed at the Safety Follow-up.
 
• Anti-AGS16C3F samples are removed at the Safety Follow-up.
 
 The AGS-16C3F Pharmacokinetic Sampling Time Points is updated as follows: 
 
• Q12W (every 12 weeks) and footnote § are removed.
 
• Safety Follow-up is removed.
 
 These assessments and time points are also removed from the study design and Sections 5.2.6.2, 5.2.7 and 5.8.
RATIONALE:
These samples are longer collected and analyzed.
3. Delete the Post Safety Follow-Up Visit
DESCRIPTION OF CHANGE:
The Post-Safety Follow-Up visit (Section 5.2.8) is removed.
RATIONALE:
The data will no longer be analyzed.
4. Update Reading of Scans
DESCRIPTION OF CHANGE:

The requirement that scans be submitted in digital format for blinded independent central review is deleted. Scans will be read on site only.

**RATIONALE:**

The data will no longer be analyzed by a blinded independent central reviewer.

**Nonsubstantial Changes**

**1. Update Key Sponsor Personnel**

**DESCRIPTION OF CHANGE:**

Contact details for the 24-hour contact for serious adverse events (SAEs), clinical research contacts and medical monitor/medical expert are revised. Section 5.7.5, Reporting Procedures for All Serious Adverse Events is updated with revised 24-hour contact information for SAEs.

**RATIONALE:**

Contact details of sponsor personnel are updated based on changes to study personnel.

**2. Update Planned Study Period**

**DESCRIPTION OF CHANGE:**

The end date of the planned study period is changed to 3Q2020.

**RATIONALE:**

This change is made to allow more time in which to complete the study.

**3. Update References**

**DESCRIPTION OF CHANGE:**

Deleted Ellenberg et al, 1985 and Wieand et al 1987 references from the Reference list.

**RATIONALE:**

The references are deleted, because they are not cited in the protocol.

**4. Minor Administrative-type Changes**

**DESCRIPTION OF CHANGE:**

Include minor administrative-type changes (e.g., typos, format, numbering and consistency throughout the protocol), update the format of the Protocol History and Investigator's Signature section for consistency with the GPF 9.0 template, and updated the style of references to conform with the Astellas Style Guide.

**RATIONALE:**

To provide clarifications to the protocol and to ensure complete understanding of study procedures.

**II. Amendment Summary of Changes:**

[figure not shown]
**IIA. Substantial Changes**

**V. Flow Chart and Schedule of Assessments**

*Figure 1 Flow Chart*

[figure not shown]
WAS:

**Figure 1 Flow Chart**

IS AMENDED TO:

**Figure 1** Flow Chart

**V. Flow Chart and Schedule of Assessments**

*Table 1 Schedule of Assessments*

WAS:

Procedures	Screen a	Cycle	Cycle 1 t				Cycles 2-4 t								C5 t	C6 t	Treatment Period beginning Cycle 7 t	Safety F/U s
			1				2	3		4								
			Week	1	1	1	3	4	7	8-9	10	10	10	12				
		Day	1	2	4	15	22	43	50-57	64	65	67	78	85	106			
Eye Symptom Questionnaire u	X		X	X u	X u	X u	X	X	X	X	X u	X u	X u	X	X	Q3W	X	
PK m (AGS-16C3F Subjects Only)			X	X	X	X	X	X		X	X	X	X		X	Q12W from C6	X	
anti-AGS-16C3F antibody formation n (AGS-16C3F Subjects Only)			X							X					X	Q12W from C6 n	X	
Disease Assessment o	X		----- Q8W from C1D1 ----->															
Bone Imaging p	X		----- Q12W from C1D1 p ----->															
Brain Imaging p	X																	
AGS-16C3F Administration q (AGS-16C3F Subjects Only)			X				X	X		X				X	X	Q3W		
Tumor Tissue r	X		----- PRN ----->															

o Disease assessments (CT and/or MRI; refer to Section 5.5) will be done every 8 weeks (± 7 days) counting from C1D1.

p Required only if clinically indicated. Post screening bone imaging will be done only for subjects with bone disease at screening. The imaging method will be any imaging modality per local or institutional standard of care (SOC) (e.g., NaF PET, MRI Bone, Tc-99 Bone Scan, etc.)

r Paraffin-embedded tumor tissue from primary or metastasis (excluding bone), for immunohistochemical studies to be conducted at a Sponsor specified CLIA certified laboratory. This is required for all non-clear cell histology subjects before Screening. Clear cell histology subjects must also provide tissue but at any point during the study. If no archive tissue is available; a biopsy may be performed to obtain tissue. Post screening, this is optional for all subjects who may have new biopsies performed.

IS AMENDED TO:																			
			Cycle 1 tr				Cycles 2-4 tr								C5 tr	C6 tr	Treatment Period beginning Cycle 7 tr	Safety F/U sq	
Procedures	Screen a	Cycle	1				2	3		4				5	6				
		Week	1	1	1	3	4	7	8-9	10	10	10	12	13	16				
		Day	1	2	4	15	22	43	50-57	64	65	67	78	85	106				
Eye Symptom Questionnaire us	X		X	X us	X us	X us	X	X	X	X	X us	X us	X us	X	X	Q3W	X		
PK m (AGS-16C3F Subjects Only)			X	X	X	X	X	X		X	X	X	X		X	<del>Q12W from C6</del>	<del>X</del>		
anti-AGS-16C3F antibody formation n (AGS-16C3F Subjects Only)			X							X					X	<del>Q12W from C6n</del>	<del>X</del>		
Disease Assessment o	X		← Q8W from C1D1 →																
Bone Imaging p	X		← Q12W from C1D1 p →																
Brain Imaging p	X																		
AGS-16C3F Administration qs (AGS-16C3F Subjects Only)			X				X	X		X				X	X	Q3W			
Tumor Tissue rp	X		← PRN →																

o Disease assessments (CT and/or MRI; refer to Section 5.5) will be done every 8 weeks (± 7 days) counting from C1D1.

p Required only if clinically indicated. Post screening bone imaging will be done only for subjects with bone disease at screening. The imaging method will be any imaging modality per local or institutional standard of care (SOC) (e.g., NaF PET, MRI Bone, Tc-99 Bone Scan, etc.)

rp Paraffin-embedded tumor tissue from primary or metastasis (excluding bone), for immunohistochemical studies to be conducted at a Sponsor specified CLIA certified laboratory. This is required for all non-clear cell histology subjects before Screening. Clear cell histology subjects must also provide tissue but at any point during the study. If no archive tissue is available a biopsy may be performed to obtain tissue. ~~Post screening, this is optional for all subjects who may have new biopsies performed.~~

**VI. PK Sampling Collection Schema**

WAS:

Table 2 AGS-16C3F PK Sampling Time Points

Cycle	Study Day	Time	Window
1	1	Predose	Anytime Predose *
		EOI	Within 2 min after EOI
		4 h †	± 15 min
	2	24 h from Day 1 †	± 4 h
	4	72 h from Day 1 †	± 1 day
	15	336 h from Day 1 †	± 4 h
2	22	Predose	Anytime Predose §
3	43	Predose	Anytime Predose §
4	64	Predose	Anytime Predose §
		EOI	Within 2 min after EOI
		4 h †	± 15 min
	65	24 h from day 64 †	± 4 h
	67	72 h from day 64 †	± 1 day
	78	336 h from day 64 †	± 4 h
6	106	Predose	Anytime Predose §
Q12W (starting at C6)		Predose	Anytime Predose §
Safety FU			At SFU Visit

IS AMENDED TO:

Table 2 AGS-16C3F PK Sampling Time Points

Cycle	Study Day	Time	Window
1	1	Predose	Anytime Predose *
		EOI	Within 2 min after EOI
		4 h †	± 15 min
	2	24 h from Day 1 †	± 4 h
	4	72 h from Day 1 †	± 1 day
	15	336 h from Day 1 †	± 4 h
2	22	Predose	Anytime Predose §
3	43	Predose	Anytime Predose §
4	64	Predose	Anytime Predose §
		EOI	Within 2 min after EOI
		4 h †	± 15 min
	65	24 h from day 64 †	± 4 h
	67	72 h from day 64 †	± 1 day
	78	336 h from day 64 †	± 4 h
6	106	Predose	Anytime Predose §
Q12W (starting at C6)		Predose	Anytime Predose §
Safety FU			At SFU Visit

**IV. Synopsis, Study Design Overview and 2 Study Objective(s), Design and Endpoints**

2.2.1 Study Design

DELETED:

~~All subjects will be followed for survival approximately every 8 weeks from the Safety Follow Up visit. This will be done by telephone, until death or study closure, whichever occurs first. A standard of care clinic visit can be used in lieu of a telephone call, if the subject is already coming to clinic.~~

**5 Treatments and Evaluation**

5.2.6.2 Cycles 5 and Beyond

WAS:

- a. Vital Signs
- b. Predose PK predose PK sample collection for AGS-16C3F subjects on Cycles 6 and every 12 weeks thereafter. Predose PK sample for Cycles 6 and every 12 weeks thereafter must be collected anytime before AGS-16C3F drug administration on the day of infusion.

IS AMENDED TO:

- a. Vital Signs
- b. ~~Predose PK predose PK sample collection for AGS-16C3F subjects on Cycles 6 and every 12 weeks thereafter. Predose PK sample for Cycles 6 and every 12 weeks thereafter must be collected anytime before AGS-16C3F drug administration on the day of infusion.~~

**5 Treatments and Evaluation**

5.2.8 Post Safety Follow-Up Visit

DELETED:

~~5.2.8 Post Safety Follow Up Visit~~

~~All subjects will be followed for survival approximately every 8 weeks from the Safety Follow Up visit. This will be done by telephone, until death or study closure, whichever occurs first. A standard of care clinic visit can be used in lieu of a telephone call, if the subject is already coming to clinic.~~

~~Those subjects who discontinued the study for reasons other than objective disease progression by RECIST v.1.1 will continue to have disease assessments every 8 weeks ( $\pm$  7 days) counting from C1D1. This will continue until subject has radiologically confirmed progression, initiates a new therapy, study closure or subject dies.~~

~~Any subjects who had a positive immunogenicity result will continue to have immunogenicity samples collected for testing every 12 weeks until it returns to negative or baseline value.~~

5 Treatments and Evaluation 5.5 Efficacy Assessment
WAS:
Scans will be read on site and also submitted in digital format for blinded independent central review. Details of scan submission to independent central radiology vendor will be provided in a separate manual.
IS AMENDED TO:
<del>Scans will be read on site, and also submitted in digital format for blinded independent central review. Details of scan submission to independent central radiology vendor will be provided in a separate manual.</del>

5 Treatments and Evaluation 5.8 Test Drug Concentration
DELETED:

<del>• Q12W (starting at Cycle 6): predose (before the AGS 16C3F infusion)</del>

<del>• Safety Follow Up visit</del>

1. INTRODUCTION

This document describes the rules and conventions to be used in the presentation and analysis of efficacy, safety, pharmacokinetic, and antibody formation data for Protocol AGS-16C3F-15-3. It describes the data to be summarized and analyzed, including specifics of the statistical analyses to be performed.

PK parameter estimation is outside the scope of this statistical analysis plan (SAP) and may be addressed by the sponsor in a separate document. Reporting of the PK concentrations and estimated parameters will be addressed in this SAP.

This SAP is based on Protocol AGS-16C3F-15-3, version 4.0 (Amendment 3, dated 18 Jul 2017) and AGS-16C3F-15-3 Subject Case Report Forms, Version 6.0 (dated 26 SEP 2017).

2. STUDY OBJECTIVES

2.1. PRIMARY OBJECTIVE

To evaluate the Progression Free Survival (PFS), based on investigator radiologic review, of AGS-16C3F compared to axitinib in subjects with metastatic renal cell carcinoma.

2.2. SECONDARY OBJECTIVES

- To evaluate the following for AGS-16C3F compared against axitinib:
 - PFS per RECIST v1.1 by blinded central radiology assessment
 - Overall Survival (OS)
 - Objective Response Rate (ORR) based on the investigator's radiographic assessment
 - Disease Control Rate (DCR) based on the investigator's radiographic assessment
 - Duration of Response (DOR) based on the investigator's radiographic assessment
 - Safety
- To evaluate the pharmacokinetics of AGS-16C3F
- To evaluate the incidence of antidrug antibody formation to human native antibody (AGS-16C3) and antibody drug conjugate (AGS-16C3F)

2.3. SAFETY OBJECTIVES

- To characterize the general safety profile of AGS-16C3F compared to axitinib, based on adverse event reports, vital sign measurements, electrocardiogram (ECG) results, and clinical laboratory results
- To monitor ocular safety, based on complete eye examinations, ocular symptoms, and clinical ocular adverse events

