### 5.2.7 Post-treatment Follow-Up Period (Safety Follow-Up visit)

All subjects will be required to have a Safety Follow-Up visit at least 28 days (+ 7 days) after the last dose. Every effort should be made to have this visit occur within the specified timeframe. If this visit cannot be performed within the specified timeframe (e.g., subject initiating new treatment, subject admitted to hospice), this visit should be scheduled as close as possible to the specified timeframe. To ensure subject's wellbeing and safety, a Safety Follow-Up visit performed outside of the window is strongly preferred over no Safety Follow-Up Visit.

Procedures below will be done during the Safety Follow-Up Visit, unless otherwise specified.

- Physical exam and body weight
- Vital signs; refer to Section 5.6.1
- ECG in triplicate (approximately 3-5 minutes in between ECGs). Ensure that the subject is in the same position for every reading; refer to Section 5.6.4
- ECOG Performance Status; refer to Appendix 12.5
- Hematology, chemistry, CRP, Thyroid Function Test, PT/aPTT, and uPCR; refer to Section 5.6.3
- Complete eye exam as clinically indicated; refer to Section 5.6.5
- Complete ESQ; refer to Section 5.6.5.1
- PK and ADA blood samples will be collected for AGS-16C3F subjects only, as specified in Table 1 and Table 2.

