### 5.6.4 Electrocardiogram (ECG)

ECGs will be done in triplicate for all timepoints, approximately 3-5 minutes between each assessment. Ensure that the subject is in the same position for every reading.

ECGs will be collected at Screening, C1D1, and at the Safety Follow-Up visits.

For subjects randomized to AGS-16C3F, on C1D1, the ECGs will be taken predose (anytime predose on actual dosing day) and again 2 hours after the end of infusion, when the total prescribed dose has been administered (e.g., 2 h after the end of infusion).

For subjects randomized to axitinib, on C1D1, the ECGs will be taken predose (anytime predose on actual dosing day) only.

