6.4. DERIVED TIMEPOINTS

For subjects in the AGS-16C3F group, each infusion date starts a new cycle. Cycles are numbered consecutively. For subjects in the axitinib group, clinic visits and most other events are identified by the planned study day.

The following derived visit definitions will apply to tables, figures, and listings unless otherwise specified for a particular analysis:

- **Worst Post-Baseline:** The worst value collected in the period from C1D1 post-dose through the later of the safety follow-up visit or the last dose date + 28 days (inclusive).
- **Safety Follow-Up:** Everyone is required to have an actual safety follow up visit and one measurement for the safety f/u. For subjects who don't have a safety F/U visit, report the worst value recorded during the period from the day of last dose or decision to end treatment through the subject's last available assessment.
- **Final Visit:** The chronologically last available assessment.
- **Any Time during Treatment/Safety Follow-up:** From C1D1 post-dose through the later of the safety follow-up visit or the last dose date + 28 days (inclusive).

Eye assessments are identified in the raw data only by the exam date. Data from the AGS-16C3F subjects will be assigned to a Cycle based on comparing the exam date to the infusion dates. Data from the axitinib subjects will be assigned to a scheduled assessment or identified as a PRN exam, based on the calculated study day of the exam (see Section 6.6, Visit Windowing Conventions).

For tables that show eye-related safety results by timepoint during the study, data from the AGS-16C3F subjects will be grouped for analysis as follows: Day 43 will include data recorded from post-dose C1D1 through Predose C3D1, inclusive; Day 106 will include data recorded from Post-dose C3D1 through Predose C6D1, inclusive; subsequent intervals will be defined similarly at 3-cycle intervals during treatment. For the axitinib subjects, the analysis periods are based on the scheduled/PRN classifications that have been assigned. For both groups, assessments that are made after the end of treatment (EOT) will be grouped together as "EOT and beyond". Both planned and PRN eye assessment data will be included in all intervals.

It may be necessary to derive other timepoint records for some analyses. Where applicable, these are specified for each analysis that requires them.

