19.4. ECG EVALUATIONS

19.4.1. ECG ASSESSMENTS

Subjects will have an ECG at screening, on C1D1, and at the end of study safety follow-up visit. Subjects who are randomized to AGS-16C3F will have an ECG at predose and at 2 hours post-dose on C1D1; subjects randomized to receive axitinib will have an ECG at predose only, on C1D1.

ECGs are done in triplicate for all timepoints, approximately 3-5 minutes between each assessment. Each set of results will be identified by a unique recorded clock time. The triplicate values may be considered individually or represented by their median, depending on the analysis. Retests and unscheduled assessments will be included, unless otherwise specified.

The following ECG parameters will be reported for this study:

- HR (bpm)
- PR Interval (msec)
- QRS Interval (msec)
- QT Interval (msec)
- QTcF Interval (msec) [derived]
- Overall assessment of ECG (Investigator's judgment):
 - o Normal
 - o Abnormal, Not Clinically Significant (ANCS)
 - o Abnormal, Clinically Significant (ACS)

Any ECG-related adverse events that are determined by the investigator or medical reviewer to have occurred will be collected on the Adverse Event CRF and reported in the AE tables, listings, and figures.

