19.4.4. ECG ANALYSIS METHODS

The ECG quantitative data will be summarized by incidence of treatment-emergent Grade 3 or Grade 4 QTcF values by treatment arm. Grade 3 and Grade 4 values will be identified prior to averaging the triplicate ECG results.

Subjects who met the abnormal criterion specified in Section 19.4.3 will be identified on the ECG data listing.

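### The pooled by-arm table of Grade 3/4 QTcF values rests on unequal ECG schedules and cannot support the ECG part of the safety comparison with axitinib

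*SAP*

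**What the plan says.** SAP 2.3 lists this objective: "To characterize the general safety profile of AGS-16C3F compared to axitinib, based on adverse event reports, vital sign measurements, electrocardiogram (ECG) results", with clinical laboratory results named next. SAP Table A explains that the safety objectives were implied by the protocol and added for clarification.

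The visits are the same in both arms (Protocol 5.6.4): "ECGs will be collected at Screening, C1D1, and at the Safety Follow-Up visits". What is done on C1D1 differs. For AGS-16C3F, "on C1D1, the ECGs will be taken predose (anytime predose on actual dosing day) and again 2 hours after the end of infusion". For axitinib, "For subjects randomized to axitinib, on C1D1, the ECGs will be taken predose (anytime predose on actual dosing day) only". SAP 19.4.1 agrees: "subjects randomized to receive axitinib will have an ECG at predose only, on C1D1". The last ECG belongs to the follow-up visit in Protocol 5.2.7: "All subjects will be required to have a Safety Follow-Up visit at least 28 days (+ 7 days) after the last dose".

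The quantitative analysis is in SAP 19.4.4: "The ECG quantitative data will be summarized by incidence of treatment-emergent Grade 3 or Grade 4 QTcF values by treatment arm". That section does not say what treatment-emergent means for an ECG. The post-baseline period in SAP 6.4 runs "from C1D1 post-dose through the later of the safety follow-up visit or the last dose date + 28 days (inclusive"), so it takes in the Safety Follow-Up tracing. SAP 19.4.1 also admits retests and unscheduled ECGs. Protocol 7.5.5 plans something different: 12-lead results by treatment group and scheduled time point.

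**The concern.** An incidence of this kind counts subjects with at least one flagged value, so it depends on how often each subject was recorded as well as on the drug. Here the two arms are recorded a different number of times, and the difference falls in the treatment period.

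Two misreadings become easy. A low axitinib figure may be taken as evidence of no QTcF effect, although no tracing was scheduled while subjects were taking it. A higher AGS-16C3F figure may be taken as a drug effect, although part of it could come from one extra recording. Neither misreading needs a p-value, and neither document mentions the imbalance. A display by scheduled time point would show it; a pooled figure hides it.

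**Working it through.** The plan states no figure for the ECG comparison, so there is none to reproduce. The check is a count, followed by a bound.

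**1. Scheduled triplicates** (Protocol Table 1 and its ECG footnote, Protocol 5.6.4, SAP 19.4.1)

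| Time point | AGS-16C3F | Axitinib | Status |
|---|---|---|---|
| Screening | 1 | 1 | before treatment |
| C1D1 predose | 1 | 1 | pre-treatment under SAP 6.3 |
| C1D1, 2 h after end of infusion | 1 | 0 | during treatment |
| Cycle 2 onward | 0 | 0 | none scheduled |
| Safety Follow-Up | 1 | 1 | 28 days or more after last dose |
| **Post-baseline total** | **2** | **1** | |
| **During treatment** | **1** | **0** | |

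Axitinib subjects attend every 21 days (Protocol 5.1.1.2). Taking the planned 4-month control median PFS as a proxy for time on treatment, 4 × 30.4375 = 121.75 days, and 121.75 / 21 = 5.8 visit intervals pass with no scheduled ECG.

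**2. What the count alone can do.** Let p be the chance of a flagged triplicate, equal at every time point and in both arms. Let c be the chance that both post-baseline triplicates of one AGS-16C3F subject are flagged. With full attendance and scheduled tracings only:

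- axitinib incidence = p
- AGS-16C3F incidence = 2p − c
- ratio = 2 − c/p

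If the two readings are fully correlated, c = p and the ratio is 1. If they are independent, c = p² and the ratio is 2 − p. Halfway, with c = p/2, it is 1.5.

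The documents give no QTcF rate, so the values of p below are assumptions. The subject counts use 134 / 2 = 67 per arm.

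| p (assumed) | Axitinib | AGS-16C3F, fully correlated | AGS-16C3F, independent | Ratio range | Subjects if independent (AGS-16C3F vs axitinib) |
|---|---|---|---|---|---|
| 1% | 1.0% | 1.0% | 1.99% | 1 to 1.99 | 1.3 vs 0.7 |
| 2% | 2.0% | 2.0% | 3.96% | 1 to 1.98 | 2.7 vs 1.3 |
| 5% | 5.0% | 5.0% | 9.75% | 1 to 1.95 | 6.5 vs 3.4 |

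**3. Attendance.** Protocol 5.2.7 foresees that some follow-up visits will be difficult to hold on time. A missed visit removes the only scheduled post-baseline ECG of an axitinib subject, while an AGS-16C3F subject keeps the 2-hour one. Suppose 80% attend (assumed), p = 2%, and all treated subjects form the denominator. Axitinib shows 0.8 × 0.02 = 1.6%. AGS-16C3F shows 2.0% if fully correlated (ratio 1.25), or 1 − 0.98 × (1 − 0.016) = 3.6% if independent (ratio about 2.2). The range of 1 to about 2 therefore applies to full attendance only.

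**4. SAP against protocol.** SAP Table A logs departures from several parts of Protocol Section 7 but has no entry for 7.5.5. The SAP was written to protocol version 4.0, whereas the protocol reviewed here is version 6.0. The available part of the Amendment 5 change summary shows no edit to that section, but version 4.0 itself was not available.

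**The case against.** The strongest reply is that little turns on this table. The introduction to SAP 19 rules out statistical comparisons of safety data unless a section specifies one, and 19.4.4 specifies none. ECG is one of four sources for a general characterisation, and the other three are untouched. ECG-related adverse events enter the adverse event tables in both arms whatever the schedule (SAP 19.4.1). SAP 19.4.3 says that a computed Grade 3 or 4 flag is not automatically an adverse event. This is a phase 2 proof-of-concept trial, the comparator is a marketed product, and the axitinib warnings listed in Protocol 1.3.2 do not include QT prolongation. An extra post-infusion ECG for the investigational drug is an understandable choice.

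All of that stands, and it limits the importance of the point. It does not make the pooled figure interpretable, because a descriptive by-arm incidence under a comparative objective will still be read across the columns.

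A second reply is that unscheduled ECGs are counted, so axitinib tracings during treatment may exist. They may, and they should be kept. But none is required, and in an open-label trial the reasons for ordering one can differ by arm, so they do not equalise ascertainment.

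**Conclusion.** The point holds for the ECG component only. Scheduled post-baseline triplicates are 2 against 1, and those during treatment 1 against 0. The pooled incidence therefore cannot carry the ECG part of the comparison in SAP 2.3, and it drops the by-time-point summary of Protocol 7.5.5 without logging the change. The counts come directly from the documents. The possible inflation, a factor of 1 to about 2, rests on equal risk per triplicate, full attendance and an unknown within-subject correlation.

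A reader might infer more than the documents support:

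- **That the schedule doubles the AGS-16C3F incidence.** Two is the upper end and needs independent readings within a subject. Repeat QTcF readings in one person are plausibly correlated, and full correlation gives no inflation.
- **That the SAP plans a formal ECG comparison.** It plans a descriptive table.
- **That the axitinib column will be empty.** It will hold the Safety Follow-Up ECG and any unscheduled tracings.
- **That the 2-hour tracing is the only AGS-16C3F ECG taken with drug present.** It is the only one scheduled during treatment. The documents give no half-life, so residual exposure at Safety Follow-Up cannot be judged.
- **That ECG must be struck from SAP 2.3.** A qualifying sentence is enough.

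**What to change.** In SAP 19.4.4, replace the single pooled incidence with a table by arm and scheduled time point, in line with Protocol 7.5.5, showing Grade 3/4 QTcF and change from baseline:

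- C1D1, 2 hours after the end of infusion: AGS-16C3F only.
- Safety Follow-Up: both arms, labelled as 28 days or more after the last dose.
- Unscheduled and retest tracings: a separate tabulated row for each arm. Leaving them to the listing would remove from the tables the only ECGs that could show axitinib subjects during treatment, along with any for-cause AGS-16C3F tracings after Cycle 1.

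Add a footnote giving the number of scheduled post-baseline triplicates in each arm. In SAP 2.3, state that ECG results are descriptive and that no between-arm conclusion about on-treatment ECG findings will be drawn. If any departure from Protocol 7.5.5 is kept, log it in Table A.

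The cost is one re-specified table, a footnote and a sentence, and the loss of the single pooled incidence figure. No ECGs or visits are added.
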